4.2.6 Analysis of exploratory endpoints

4.2.6.1 Analysis of AO

Change from baseline in AO parameters (R5, R20, R5-R20, AX) will be analysed using MMRM (see Section 4.1.2). LS Mean change from baseline and two-sided 80% CI for each visit through Week 16 in AO parameters will be presented in figures.

Observed values and change from baseline through Week 16 will be descriptively summarised for all AO parameters by treatment groups for the ITT population.

AO parameters will be also reported in listing for the ITT population.

4.2.6.2 Analysis of FEV₁% reversibility and FEF₂₅₋₇₅%

The difference in mean change from baseline in FEV₁ % reversibility (see Section 3.6.3) through Week 16 will be estimated using a MMRM, similar to that described for the primary efficacy analysis (Section 4.1.2). The change from baseline through Week 16 will be included in the model.

The FEF₂₅₋₇₅% will also be analysed in the same way.

4.2.6.3 Analysis of asthma exacerbation

Time to first asthma exacerbation will be analysed using a Cox proportional hazard model, with treatment group, geographic region and baseline ICS total daily dose as covariates (see Section 4.1.6). The data will also be displayed in a Kaplan-Meier plot.

Number of exacerbations, total follow-up time and annual exacerbation rate including the two-sided 80% CI will be summarised by treatment group for the ITT population. Asthma exacerbations during the intervention period (baseline to last dose date +28 days) will be analysed using negative binomial model (see Section 4.1.5). Rate ratio from MEDI3506 **CCI** mg compared to placebo and from MEDI3506 **CCI** mg compared to placebo will be displayed. Similarly, the hospitalised asthma exacerbations will also be analysed.

Asthma exacerbations and hospitalised asthma exacerbations will be also reported in listing for the ITT population.

4.2.6.4 Analysis of PGI-BR

The results of the 5-item questionnaire of the PGI-BR will be descriptively summarised at Week 16 by treatment group for the ITT population.

PGI-BR responses will be also reported in listing.

4.2.6.5 Analysis of SNOT-22

The total SNOT-22 score and the change from baseline will be descriptively summarised by visit and by treatment group for the ITT population.

Total SNOT-22 score as well as single questions will be also reported in listing for the ITT population.

Change from baseline through Week 16 in SNOT-22 score will be analysed using MMRM (see Section 4.1.2). LS Mean change from baseline and two-sided 80% CI through Week 16 in SNOT-22 score will be presented in figures.

4.2.6.6 Analysis of diary data and home spirometry

2-weekly mean asthma symptom score, 2-weekly mean rescue medication usage, 2-weekly mean night time awakening due to asthma, 2-weekly mean home FEV₁ and 2-weekly mean

home PEF as derived in Section 3.6.2 through Week 24 and the changes from baseline through Week 24 will be descriptively summarised using the ITT population.

Additionally, change from baseline will be analysed using MMRM (see Section 4.1.2). The LSmean changes from baseline and two-sided 80% CI through Week 24 will be presented in figures.

2-weekly means will be also reported in listing for the ITT population.

4.2.7 Analysis of safety endpoints

Duration of exposure as calculated in Section 3.1.6 will be summarised by treatment groups for the As-treated population.

CCI

Number and percentage of participants who received planned starting dose, who received different starting dose from planned, who had any interruption or 1, 2, 3, etc. interruption will be summarised by treatment group for the As-treated population. Reason for interruption will also be provided.

Interruption will be defined as any administration where action taken is reported as 'Drug interrupted'.

A listing of the administration of investigational product together with the duration of exposure will be presented for all subjects belonging to the As-treated population.

4.2.7.1 Analysis of AEs

All AE summary tables and listings will be created by treatment group and for total MEDI3506 for the As-treated population, unless otherwise specified. AEs occurred during study intervention (on-treatment phase as defined in section 3.1.4) and follow-up period (follow-up phase as defined in section 3.1.4) will be reported in summary tables. All AEs, including AEs for enrolled but not randomised participants and for participants who were not exposed to treatment, will be listed.

An overall summary table will be produced by treatment group and for total MEDI3506 showing the number and percentage of participants with at least one AE in any of the following categories:

- AEs;
- AEs with toxicity grade 4 or 5;
- Serious adverse events (SAEs);

- Deaths due to AE;
- AEs leading to discontinuation of IP;
- AEs leading to dose interruption;
- AEs leading to withdrawal from study;
- AESI.

The total number of AEs in the different AE categories in terms of AE counts (ie, accounting for multiple occurrences of the same event in a subject) will also be presented by treatment group and for total MEDI3506.

Number and percentage of participants with at least one AE by SOC term will be produced by treatment group and for total MEDI3506.

Number and percentage of participants with at least one AE by PT will be produced for AEs with a frequency of > 5% by treatment group and for total MEDI3506. Frequency will be defined according to percentage in total MEDI3506.

Number and percentage of participants with AE by SOC and PT will be summarised by treatment group and for total MEDI3506.

Number and percentage of participants with AE by PT and maximum reported toxicity grade will be summarised by treatment group and for total MEDI3506 in table and AEs with frequency of >5% per treatment group will be graphically displayed using bar graphs. Each participant is represented only for the maximum reported intensity of each PT. Frequency will be defined according to percentage in total MEDI3506.

Number and percentage of participants with AEs by PT and investigator's causality assessment will be summarised by treatment group and for total MEDI3506.

Total number of AEs by SOC and PT will be summarised by treatment group and for total MEDI3506. Total number of SAEs by SOC and PT will be summarised by treatment group and for total MEDI3506.

Number and percentage of participants with AE leading to dose interruption by SOC and PT will be summarised by treatment group and for total MEDI3506.

Number and percentage of participants with non-serious AEs and number of non-serious events occurring in more than 5% of participants will be summarised by SOC and PT.

Number and percentage of participants with AE with outcome of death by SOC and PT will be summarised by treatment group and for total MEDI3506. Key subject information for

participants experience AEs with outcome of death will be produced for each treatment group using following information:

- Treatment group
- Subject identifier
- Sex
- Age (years)
- Event term as reported by the investigator
- PT
- Time from first IP administration to onset of AE (days) as derived in Section 3.1.6.6
- Treatment period
- Time from last IP administration to death (days) as derived in Section 3.1.6.9
- Time from first IP administration to death (days) as derived in Section 3.1.6.8
- Received treatment for AE
- Reasonable possibility AE caused by IP

Number and percentage of participants with SAE by SOC and PT will be summarised by treatment group and for total MEDI3506. Key subject information for participants experience SAEs will be produced using following information:

- Treatment group
- Subject identifier
- Sex
- Age (years)
- Event term as reported by the investigator
- PT
- Time from first IP administration to onset of AE (days) as derived in Section 3.1.6.6
- Time from last IP administration prior to AE start date, calculated for AEs starting after the discontinuation of the IP.
- Time from start of IP administration to becoming serious
- Outcome
- Action taken with IP
- Reasonable possibility AE caused by IP.

Number and percentage of participants with AE leading to discontinuation of IP by SOC and PT will be summarised by treatment group and for total MEDI3506. Key subject information for participants experience AEs leading to discontinuation of IP will be produced using following information:

- Treatment group
- Subject identifier
- Sex
- Age
- AE as reported by the investigator
- PT
- Time from first IP administration to AE onset
- Time from first IP administration to discontinuation of IP
- Seriousness
- Outcome
- Reasonable possibility AE caused by IP.

Number and percentage of participants with AESIs by maximum reported toxicity grade will be summarised by treatment group and for total MEDI3506. A list of PTs for AESIs experienced during the study will be produced. Number of participants with injection site reaction (ISR) by maximum reported toxicity grade will be summarised by treatment group and for total MEDI3506.

Number of subjects with COVID-19 related AESIs by maximum reported toxicity grade will be summarised by treatment group and for total MEDI3506. Similar table will be repeated for the number of subjects with COVID-19 related serious AESIs.

All AEs will be listed as well as AEs among ADA positive participants.

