1.3 Number of participants

A sample size of 216 participants (72 participants per treatment group), randomised 1:1:1 to MEDI3506 **CC1** mg: MEDI3506 **CC1** mg: placebo, will provide at least 80% power to detect a statistically significant difference in change from baseline to Week 16 in pre-BD FEV₁, assuming a difference of 150 mL between placebo and MEDI3506, a between-participant SD of 420 mL and a one-sided- 10% alpha level. To allow for 5% participants being ineligible for the primary analysis, a total of approximately 228 participants will be randomised in the study (approximately 76/arm).

Up to 60 participants are intended to be included in the cough sub-study (approximately 20 participants per treatment group). However, given the exploratory nature of the sub-study and that it may not be activated in all countries, randomisation of participants not included in the sub-study will not be restricted, therefore, sub-study recruitment may not be achieved. Since limited data are available on cough monitoring in this population, the sub-study is considered exploratory and no formal power calculations have been performed.

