14.3.2 All adverse events		
Table 14.3.2.1	Number of subjects with adverse events in any category	As-treated population
Table 14.3.2.2	Adverse events in any category - event counts	As-treated population
Table 14.3.2.3	Number of subjects with adverse events, most common (frequency of > 5%), by preferred term	As-treated population
Table 14.3.2.4	Number of subjects with adverse events by system organ class and preferred term	As-treated population
Table 14.3.2.5	Number of subjects with adverse events by preferred term and maximum reported toxicity grade	As-treated population
Figure 14.3.2	Adverse events, with a frequency of > 5% by preferred term and maximum reported toxicity grade	As-treated population
Table 14.3.2.6	Number of subjects with adverse events, by preferred term and relationship as assessed by investigator	As-treated population

Table 14.3.2.7	Number of adverse events, by system organ class and preferred term	As-treated population
Table 14.3.2.8	Number of subjects with adverse events, leading to dose interruption, by system organ class and preferred term	As-treated population
FDAAA1	Non-serious adverse events occurring in greater than 5% of subjects	As-treated population

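### The >5% rule for the common-AE table and bar graph uses pooled MEDI3506 only: it can omit a term above 5% in one dose arm or on placebo, and it contradicts the figure text

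*SAP*

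**What the plan says.** SAP 4.2.7.1 plans a table of participants by preferred term "for AEs with a frequency of > 5% by treatment group and for total MEDI3506", followed by the statement "Frequency will be defined according to percentage in total MEDI3506". Two paragraphs later it plans a summary by preferred term and maximum toxicity grade, and says that "AEs with frequency of >5% per treatment group will be graphically displayed using bar graphs". The same definition by total MEDI3506 is then repeated.

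SAP Appendix C lists the two outputs as Table 14.3.2.3, "Number of subjects with adverse events, most common (frequency of > 5%), by preferred term", and Figure 14.3.2, "Adverse events, with a frequency of > 5% by preferred term and maximum reported toxicity grade". Neither title says which group the percentage refers to.

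The same section plans four further tables with no frequency threshold, each by treatment group and for total MEDI3506:

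- participants by system organ class and preferred term (14.3.2.4);
- participants by preferred term and maximum grade (14.3.2.5);
- participants by preferred term and investigator causality (14.3.2.6);
- event counts by system organ class and preferred term (14.3.2.7).

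All AEs are also listed.

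**The concern.** There are two problems, one of wording and one of substance.

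**Wording.** For the figure, the threshold is first stated per treatment group and then defined on the two dose arms combined. These rules select different sets of terms, so a programmer cannot follow both.

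**Substance.** Each display has a column or bar per arm, but which terms enter is decided only by the combined active arms. A term concentrated in one dose is judged against a denominator twice the size of that arm. Placebo plays no part in selection. Yet the trial has two doses, its safety objective is a comparison with placebo (SAP 1.1), and the protocol names choice of dosing regimen among the uses of the safety endpoints (Protocol 4.2.1.2). Protocol 8.3.4 also has clinically significant worsening of asthma reported as an AE, so a term that is more frequent on placebo than on active treatment is a realistic possibility. What is at stake is whether a reader of these two displays sees such a term there.

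**Working it through.** **Inputs**

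- Threshold: strictly above 5% (SAP 4.2.7.1).
- Selection denominator: both MEDI3506 arms together (SAP 4.2.7.1).
- Arm size: "A sample size of 216 participants (72 participants per treatment group), randomised 1:1:1 to MEDI3506" with 72 evaluable per arm, and about 228 randomised, or 76 per arm (SAP 1.3). AE tables use the As-treated population, whose actual size is not given, so 72 and 76 serve as the planned range.

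**The plan's own figure.** Difference 150 mL, SD 420 mL, one-sided alpha 10%:

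- standard error = 420 × √(2/72) = 70 mL, so the standardised difference is 150/70 = 2.143;
- power = Φ(2.143 − 1.282) = Φ(0.861) ≈ 0.805, in line with the stated 80% or more;
- 216/0.95 = 227.4, rounded up to 228, or 76 per arm.

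The arm sizes reproduce.

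**Largest count omitted under the pooled rule.** Find the largest x with x/(2n) ≤ 5%, then place all x in one dose arm.

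| n per arm | pooled 2n | largest omitted x | pooled % | % of one arm if all there | smallest x shown |
|---|---|---|---|---|---|
| 72 | 144 | 7 | 4.9% | 9.7% | 8 (5.6% pooled) |
| 76 | 152 | 7 | 4.6% | 9.2% | 8 (5.3% pooled) |

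At 76 per arm, counts of 4 to 7 in one dose arm with none in the other are 5.3% to 9.2% of that arm and 2.6% to 4.6% pooled. All are omitted.

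**Less extreme splits of seven cases (76 per arm).** 6 versus 1 is 6/76 = 7.9% of the higher arm; 5 versus 2 is 5/76 = 6.6%. Both are 7/152 = 4.6% pooled and are omitted.

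**Placebo.** A term seen only on placebo is 0/152 = 0% of total MEDI3506 and is omitted whatever its placebo frequency. As an illustration with assumed counts, 10/76 = 13.2% on placebo against 7/152 = 4.6% on MEDI3506 would also be omitted.

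**How often this could happen.** Let the number of cases in each dose arm be binomial with assumed true rates p1 and p2. The chance of omission is the probability that the two counts sum to 7 or fewer.

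| assumed rates (one dose, other dose) | 76 per arm | 72 per arm |
|---|---|---|
| 9%, 0% | 0.62 | 0.68 |
| 9%, 1% | 0.51 | 0.57 |
| 8%, 1% | 0.62 | 0.68 |
| 10%, 0% | 0.51 | 0.57 |

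**Under a rule of above 5% in any treatment group.** A term enters at 4 cases in any arm (4/76 = 5.3%; 4/72 = 5.6%). The largest single-arm frequency omitted falls to 3/76 = 3.9% or 3/72 = 4.2%. With a true rate of 9% in one arm, that arm alone brings the term in with probability 0.92 (n = 76) or 0.90 (n = 72).

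**Nothing now shown is dropped.** With equal arms the pooled percentage is the average of the two dose-arm percentages, so if it exceeds 5% at least one dose arm does too.

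**The case against.** The strongest reply is that this is a display preference. A term with 7 cases against 0 appears by arm in four complete tables, and the bar graph is a filtered picture of Table 14.3.2.5, which is complete. SAEs, deaths, discontinuations, AESIs and injection site reactions have their own outputs. No test, endpoint or stopping rule depends on the filter. Selecting terms by frequency on the investigational drug is a coherent way to describe that drug's common AEs, and the words per treatment group in the figure sentence might describe only how the bars are laid out. At the low end, 4/76 against 0/76 is weak evidence in any case (two-sided Fisher p about 0.12), while 8 against 0 already passes the pooled filter.

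Most of this stands, and it rules out several stronger readings:

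- A reader might infer that dose-related events are hidden from the report. They are not; all terms are tabulated by arm and all AEs are listed.
- A reader might infer that pooling halves the rates displayed. It does not; it affects only which terms enter, and per-arm percentages remain undiluted.
- A reader might treat these as the headline safety displays. Neither document gives them that status.
- A reader might extend the point to the non-serious AE table (FDAAA1). Its rule refers to more than 5% of participants and carries no pooled-MEDI3506 definition, so the same defect is not shown there.

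The reply does not remove the conflict in the figure paragraph, whose more natural reading is a threshold applied per group. Nor does it explain why selection in a two-dose, placebo-controlled comparison should ignore the frequency in each single dose and on placebo.

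**Conclusion.** The point holds as a minor weakness in how terms are selected for two descriptive displays, together with contradictory wording for one of them. On the planned 72 to 76 per arm, a term can be left out of Table 14.3.2.3 and Figure 14.3.2 although up to 7 participants in one dose arm had it. The 9.2% to 9.7% upper end requires no cases at all in the other dose arm, and each case there lowers it by one participant. A term confined to placebo is never selected.

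The result rests on planned equal arms and on the explicit pooled definition being the one that is programmed. The omission probabilities rest in addition on assumed true rates. No AE data are lost and no inference changes.

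**What to change.** In SAP 4.2.7.1, replace both occurrences of the pooled-frequency sentence with: 'Preferred terms with a frequency >5% in any treatment group (either dose or placebo) will be shown.' Reword the figure sentence so that it refers to the same rule. Apply this to Table 14.3.2.3 and Figure 14.3.2. Leave the rule for the non-serious AE table (FDAAA1) unchanged.

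The cost is one replacement sentence in two places, a matching edit to the figure sentence, and a slightly longer table and figure, since some terms with only four cases in a single arm will now enter.

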4.2.7.2 Analysis of vital signs

Observed values and change from baseline in vital signs will be summarised by treatment group and for total MEDI3506, and visit. Key subject information will be produced for vital sign parameters treatment-emergent changes outside predefined criteria (Table).

Individual vital sign results will be listed.

4.2.7.3 Analysis of laboratory measurements

Laboratory evaluations (haematology, clinical chemistry and quantitative urinalysis parameters as per Table) will be summarised with descriptive statistics at each visit and change from baseline summarised for each post-baseline visit by treatment group and for total MEDI3506. Categorical haematology, clinical chemistry and urinalysis results will be summarised in shift tables comparing maximum value during treatment with baseline value by treatment group and for total MEDI3506. Similarly, haematology and clinical chemistry results will also be summarised in shift tables comparing minimum value during treatment.

ALT or AST versus total bilirubin, expressed as multiples of ULN as well as liver biochemistry test results over time – participants with elevated ALT or AST, and elevated total bilirubin at any point during the study following the start of study medication will be presented in figures.

In addition to the summaries above also the maximum on-treatment ALT and AST by maximum total bilirubin for assessing Hy's law criteria will be presented by treatment group and for total MEDI3506.

All laboratory results will be listed as well as any SARS-CoV-2 test results.

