9.4.4 Safety

The occurrence of AEs and SAE will be described by System Organ Class, Preferred Term, severity, and relationship to the study intervention. Participants will be counted only once for each preferred term, once for each system organ class, and by the highest severity of an event. Number of participants with elevated liver function tests that meet the HL definition will be evaluated. Laboratory evaluations will be summarised with descriptive statistics at each visit and change from baseline summarised for each post-baseline visit. Laboratory measurements will also be summarised based on the number and percentage of participants above or below a pre-specified threshold for each test. The number of participants with clinically significant abnormal ECG results based on investigators' judgments will be summarised at each visit. Change from baseline in vital signs will be summarised by visit.

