Appendix E Actions Required in Cases of Increases in Liver Biochemistry and Evaluation of Hy's Law

E 1 Introduction

This Appendix describes the process to be followed in order to identify and appropriately report PHL and HL cases. It is not intended to be a comprehensive guide to the management of elevated liver biochemistries.

During the course of the study, the investigator will remain vigilant for increases in liver biochemistry. The investigator is responsible for determining whether a participant meets PHL criteria at any point during the study.

All sources of laboratory data are appropriate for the determination of PHL and HL events; this includes samples taken at scheduled study visits and other visits including central and all local laboratory evaluations even if collected outside of the study visits; for example, PHL criteria could be met by an elevated ALT from a central laboratory **and/or** elevated TBL from a local laboratory.

The investigator will also review AE data (for example, for AEs that may indicate elevations in liver biochemistry) for possible PHL events.

The investigator participates, together with AstraZeneca clinical project representatives, in review and assessment of cases meeting PHL criteria to agree whether HL criteria are met. HL criteria are met if there is no alternative explanation for the elevations in liver biochemistry other than DILI caused by the IMP.

The investigator is responsible for recording data pertaining to PHL/HL cases and for reporting SAEs and AEs according to the outcome of the review and assessment in line with standard safety reporting processes.

E 2 Definitions

Potential Hy's Law

AST or ALT $\geq 3 \times$ ULN **together with** TBL $\geq 2 \times$ ULN at any point during the study following the start of study medication irrespective of an increase in ALP.

Hy's Law

AST or ALT $\geq 3 \times$ ULN **together with** TBL $\geq 2 \times$ ULN, where no other reason, other than the IMP, can be found to explain the combination of increases, eg, elevated ALP indicating cholestasis, viral hepatitis, another drug.

For PHL and HL the elevation in transaminases must precede or be coincident with (ie, on the same day) the elevation in TBL, but there is no specified timeframe within which the elevations in transaminases and TBL must occur.

E 3 Identification of Potential Hy's Law Cases

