Period 4: Evening of Day 43 – Morning of Day 57	Week 8	57
Period 5: Evening of Day 57 – Morning of Day 71	Week 10	71
Period 6: Evening of Day 71 – Morning of Day 85	Week 12	85
Period 7: Evening of Day 85 – Morning of Day 99	Week 14	99
Period 8: Evening of Day 99 – Morning of Day 113	Week 16	113
Period 9: Evening of Day 113 – Morning of Day 127	Week 18	127
Period 10: Evening of Day 127 – Morning of Day 141	Week 20	141
Period 11: Evening of Day 141 – Morning of Day 155	Week 22	155
Period 12: Evening of Day 155 – Morning of Day 169	Week 24	169

The Early Discontinuation and unscheduled visits will be included when applying the visit windows to ensure that all available data are used in the analysis.

For bi-weekly summaries, the mean of all non-missing observations within an assigned window is calculated. If there are fewer than 10 completed days in the 14 day period (where a

complete day = entry from the evening AND the following morning) then the analysis value will be set to missing.

Finally, for the purpose of the statistical analysis, the assessments will be allocated to the study phase in which they are collected as reported below.

Table 2 Study phase windows

Study phase	Phase Window for Analysis (Days)
Pre-treatment	Prior to the first administration of investigational product (day <1 ^a)
On-treatment	≥ day 1 ^b to last dose date plus 28 days (included)
Follow-up	> last dose date plus 28 days

^a Includes all measurements collected before first dose of IP. If the measurement is collected on day 1 it cannot be determined if it was done before or after the first dose of IP (due to missing time and/or planned time point), then it will be considered as collected after first dose of IP.

^b Includes all measurements collected on the day of first dose of IP, at the time of IP intake and after.

Unless otherwise specified, the study phase will be mainly used for safety analysis (e.g., laboratories, adverse events) and for CompEx analysis.

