14.3.7 Clinical laboratory evaluation		
Table 14.3.7.1.1	Haematology parameters over time	As-treated population
Table 14.3.7.1.2	Haematology parameters, baseline to maximum value during treatment	As-treated population
Table 14.3.7.1.3	Haematology parameters, baseline to minimum value during treatment	As-treated population
Table 14.3.7.2.1	Clinical chemistry parameters over time	As-treated population

Table 14.3.7.2.2	Clinical chemistry parameters, baseline to maximum value during treatment	As-treated population
Table 14.3.7.2.3	Clinical chemistry parameters, baseline to minimum value during treatment	As-treated population
Table 14.3.7.2.4	Subjects with potential Hy's Law - individual subject data	As-treated population
Figure 14.3.7.2.1	ALT versus total bilirubin, expressed as multiples of ULN	As-treated population
Figure 14.3.7.2.2	AST versus total bilirubin, expressed as multiples of ULN	As-treated population
Table 14.3.7.2.5	Maximum on-treatment ALT and AST by maximum total bilirubin for assessing Hy's Law criteria	As-treated population
Figure 14.3.7.2.3	Liver biochemistry test results over time - subjects with elevated ALT or AST, and elevated total bilirubin, at any point during the study following the start of study medication	As-treated population
Table 14.3.7.3.1	Urinalysis parameters over time	As-treated population
Table 14.3.7.3.2	Urinalysis parameters, baseline to maximum value during treatment	As-treated population

Table 14.3.7.3.3	Urinalysis parameters, baseline versus maximum observation on treatment, shift table	As-treated population

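### The by-arm laboratory count for Hy's Law (SAP Table 14.3.7.2.5) uses a shorter period than the protocol's Potential Hy's Law definition and no order rule, so it can miss late cases and count bilirubin-first ones

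*SAP*

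**What the plan says.** Protocol 9.4.4 makes the commitment: "Number of participants with elevated liver function tests that meet the HL definition will be evaluated".

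Protocol Appendix E 2 gives two definitions. PHL is AST or ALT at least 3 times ULN together with TBL at least 2 times ULN, "at any point during the study following the start of study medication irrespective of an increase in ALP". Hy's Law (HL) adds that nothing other than the study drug explains the combination. For both, the transaminase elevation "must precede or be coincident with (ie, on the same day) the elevation in TBL", and no limit is set on the interval between the two. Appendix E 1 accepts central and local laboratory results alike.

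SAP 4.2.7.3 plans, by treatment group and for total MEDI3506, the "maximum on-treatment ALT and AST by maximum total bilirubin for assessing" the Hy's Law criteria. The output list in SAP Appendix C repeats this as Table 14.3.7.2.5 ("Maximum on-treatment ALT and AST by maximum total bilirubin for assessing" the criteria). SAP 3.1.4 ends the on-treatment phase at last dose plus 28 days; follow-up is everything "> last dose date plus 28 days".

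**The concern.** The table offered for assessing Hy's Law by arm does not apply the protocol's laboratory rule.

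- **Period.** ALT/AST count only up to last dose plus 28 days, while Appendix E 2 runs on after that. The preceding paragraph of SAP 4.2.7.3 describes a liver figure that does use the any-time period. SAP Section 6, which lists changes from the protocol, does not mention the shorter window.
- **TBL period.** The on-treatment qualifier is attached to ALT and AST only, so the text does not settle which bilirubin results enter.
- **Order.** Two separate maxima cannot show which rose first, so a bilirubin-first participant falls in the same cell as a PHL case. This is foreseeable: Exclusion Criterion 15(b) exempts raised bilirubin due to Gilbert's disease.

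Hy's Law is the first-listed adverse event of special interest. At stake is whether the by-arm laboratory comparison counts the right participants, above all those who stop dosing early and whose liver tests rise later.

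**Working it through.** No stated figure in the plan bears on this point. The check compares the table's window with the chemistry schedule, then applies both rules to the same patterns.

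**Inputs.** Chemistry is scheduled after baseline at SV6, SV7, SV8, SV9, SV10 and SV12, nominal Days 8, 29, 57, 85, 113 and 169, plus an early-discontinuation visit (SAP 3.5.3; Protocol Table 2). Dosing-day vital signs are placed at SV4, SV7, SV8 and SV9 (SAP 3.5.2), so a completer's last dose is nominally on Day 85. On-treatment ends at last dose + 28 (SAP 3.1.4).

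**Step 1: what the window leaves out.** End of window = last dose day + 28; days outside = 169 − end.

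| Last dose | Window ends | Scheduled chemistry outside | Days outside |
|---|---|---|---|
| Day 85 | Day 113 | SV12 | 56/169 = 33% |
| Day 57 | Day 85 | SV10, SV12 | 84/169 = 50% |
| Day 29 | Day 57 | SV9, SV10, SV12 | 112/169 = 66% |
| Day 1 | Day 29 | SV8, SV9, SV10, SV12 | 140/169 = 83% |

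The visit windows matter too. With SV9 dosing on any of Days 82 to 88 and SV10 on any of Days 110 to 116, the SV10 sample is outside whenever the SV10 day exceeds the SV9 day + 28. That holds for 21 of the 7 × 7 = 49 day pairs.

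**Step 2: the two rules on the same patterns.** Take a completer on nominal days, one visit with ALT at least 3 times ULN and one with TBL at least 2 times ULN. There are 6 × 6 = 36 pairs. Appendix E 2 accepts a pair when the ALT day is on or before the TBL day: 6 + 5 + 4 + 3 + 2 + 1 = 21 qualify and 15 do not.

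- *Both maxima on-treatment:* any pair with TBL at Day 169 is lost. That misses 6 of the 21 and keeps 15.
- *Only ALT/AST on-treatment, TBL at any time:* the one qualifying pair lost has both elevations at Day 169. That misses 1 of the 21 and keeps 20.
- *Either reading:* bilirubin-first pairs with ALT by Day 113 are counted: 4 + 3 + 2 + 1 = 10 of the 15 non-qualifying pairs.

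These are counts of patterns, not expected patients.

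**Examples.** ALT 4 times and TBL 2.5 times ULN, both first seen at Day 169, is PHL but is not in the table on either reading. TBL 2.5 times ULN at Day 29 only, then ALT 4 times ULN at Day 85, is not PHL but is in the table.

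**The case against.** The strongest reply is that the table is not the only route by which cases reach a by-arm display. Each PHL case is reported as an SAE (Appendix E 4.2), and cases with no other explanation are re-termed Hy's Law (Appendix E 5). Hy's Law is also an AESI category. SAEs and AESIs are tabulated by arm, and the AE summaries include follow-up (SAP 4.2.7.1). Table 14.3.7.2.4 gives individual PHL subjects, Figure 14.3.7.2.3 covers any time after first dose, and all laboratory results are listed. The cross-table is described as additional to these and works as a screen.

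That stands against inferring that this is the only by-arm Hy's Law output, or that late cases would vanish from the report. It does not supply the missing count. The SAE tables follow reported terms, which are revised when another cause is agreed. The AESI table rests on an investigator checkbox with a MedDRA cross-check, and the SAP does not say it is split by category. The individual table and the figure are not specified as by-arm counts.

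Two further points stand. A reader might infer that the table should deliver the HL count promised in Protocol 9.4.4. No laboratory table can, because HL needs case review to exclude other causes; the laboratory rule is PHL. And crossing maxima from different days is not itself an error, since the protocol sets no limit on the interval. Only the missing order rule is.

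**Conclusion.** The mismatch holds. The only by-arm laboratory-based Hy's Law count departs from Appendix E 2 on period and order and leaves the TBL period open. It can miss PHL arising in follow-up and can count bilirubin-first participants. Whether it does either depends on the data, so a reader should not infer that the count will be wrong.

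The size is modest for completers: one of six scheduled post-baseline chemistry visits on nominal days, sometimes two given the visit windows. It grows to between two and four visits after early stopping, assuming those participants attend the later scheduled visits; any early-discontinuation sample is extra. The percentages in the working are shares of calendar days and should not be read as shares of cases missed. The documents give no expected number of liver cases, so none is assumed. No efficacy result is affected.

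**What to change.** In SAP 4.2.7.3 and Table 14.3.7.2.5:

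1. Add a by-arm row labelled as Potential Hy's Law per Protocol Appendix E 2. Use all central and local results, scheduled and unscheduled, from first dose to end of study (on-treatment plus follow-up). Count participants with ALT or AST at least 3 times ULN and TBL at least 2 times ULN whose first ALT/AST elevation is on or before the day of their first TBL elevation.
2. Show separately those whose TBL was already at least 2 times ULN before the transaminase rise, including at baseline. Merely requiring a high TBL on or after the day of the transaminase rise would not be enough: ALT, AST and TBL are tested concurrently, so bilirubin that was high beforehand and stayed high would still be counted.
3. State the TBL period for the existing cross-table and keep that table as a screening display.
4. Label the row PHL, not HL.

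The cost is SAP wording and one extra row, with the separate group shown beside it. No new data are needed: Appendix E 3 already sends local results that meet the identification criteria to the eCRF.
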